### **Secondary Endpoint**

OS rates at 12 and 24 months will be derived from the Kaplan Meier estimate and corresponding confidence interval will be derived based on Greenwood formula for variance derivation and on log-log transformation applied on the survivor function.

PFS based on investigator assessment will be analyzed in the first 558 subjects, all randomized subjects and all randomized subjects who did not receive corticosteroids at baseline.

All secondary endpoints will be analyzed at the same time as the OS and PFS primary analyses using the analysis methods already defined in the SAP.

**1 INTRODUCTION**

[figure not shown]

[figure not shown]

[figure not shown]

[figure not shown]

## 1.2 Research Hypothesis

Addition of nivolumab to standard radiotherapy (RT) plus temozolomide (TMZ) will increase PFS in subjects with newly-diagnosed GBM of MGMT-methylated or indeterminate subtypes and will increase OS in subjects with newly-diagnosed GBM of MGMT-methylated or indeterminate subtypes without baseline corticosteroids and regardless of baseline corticosteroids.

[figure not shown]
## 1.3 Objective(s)

[figure not shown]
### 1.3.1 Primary Objectives

[figure not shown]
- To compare PFS of subjects with newly-diagnosed MGMT-methylated or indeterminate GBM subtypes treated with RT plus TMZ combined with nivolumab or placebo. PFS will be determined by blinded independent central review (BICR) based on RANO criteria.
- To compare OS of subjects with newly-diagnosed MGMT-methylated or indeterminate GBM subtypes without baseline corticosteroids and regardless of baseline corticosteroids (ie, all comers) treated with RT plus TMZ combined with nivolumab or placebo.

[figure not shown]
### 1.3.2 Secondary Objectives

- To compare OS of subjects with newly-diagnosed MGMT-methylated or indeterminate GBM subtypes without baseline corticosteroids and regardless of baseline corticosteroids (ie, all comers) treated with RT plus TMZ combined with nivolumab or placebo at 12 and 24 months.
- To compare PFS based on investigator assessment by RANO criteria of subjects with newly-diagnosed MGMT methylated or indeterminate GBM subtypes treated with RT plus TMZ combined with nivolumab or placebo.

## **2 ETHICAL CONSIDERATIONS**

### **2.1 Good Clinical Practice**

This study will be conducted in accordance with Good Clinical Practice (GCP), as defined by the International Conference on Harmonisation (ICH) and in accordance with the ethical principles

underlying European Union Directive 2001/20/EC and the United States Code of Federal Regulations, Title 21, Part 50 (21CFR50) and applicable local requirements.

The study will be conducted in compliance with the protocol. The protocol and any amendments and the subject informed consent will receive Institutional Review Board/Independent Ethics Committee (IRB/IEC), if applicable, also by local health authority approval/favorable opinion prior to initiation of the study.

All potential serious breaches must be reported to Sponsor or designee immediately. A serious breach is a breach of the conditions and principles of GCP in connection with the study or the protocol, which is likely to affect, to a significant degree, the safety or physical or mental integrity of the subjects of the study or the scientific value of the study.

Personnel involved in conducting this study will be qualified by education, training, and experience to perform their respective tasks.

This study will not use the services of study personnel where sanctions have been invoked or where there has been scientific misconduct or fraud (eg, loss of medical licensure, debarment).

## **2.2 Institutional Review Board/Independent Ethics Committee**

Before study initiation, the investigator must have written and dated approval/favorable opinion from the IRB/IEC and Regulatory Authority(ies), if required by local legislation for the protocol, consent form, subject recruitment materials (eg, advertisements), and any other written information to be provided to subjects. The investigator or BMS should also provide the IRB/IEC or local health authority with a copy of the Investigator Brochure or product labeling information to be provided to subjects and any updates.

The investigator, Sponsor or designee should provide the IRB/IEC or local health authority with reports, updates and other information (eg, expedited safety reports, amendments, and administrative letters) according to regulatory requirements or institution procedures.

## **2.3 Informed Consent**

Investigators must ensure that subjects are clearly and fully informed about the purpose, potential risks, and other critical issues regarding clinical studies in which they volunteer to participate.

In situations where consent cannot be given to subjects, their legally acceptable representatives (as per country guidelines) are clearly and fully informed about the purpose, potential risks, and other critical issues regarding clinical studies in which the subject volunteers to participate.

Sponsor or designee will provide the investigator with an appropriate (ie, Global or Local) sample informed consent form which will include all elements required by ICH, GCP and applicable regulatory requirements. The sample informed consent form will adhere to the ethical principles that have their origin in the Declaration of Helsinki.

Investigators must:

- Provide a copy of the consent form and written information about the study in the language in which the subject is most proficient prior to clinical study participation. The language must be non-technical and easily understood.
- Allow time necessary for subject or subject's legally acceptable representative to inquire about the details of the study.
- Obtain an informed consent signed and personally dated by the subject or the subject's legally acceptable representative and by the person who conducted the informed consent discussion.
- Obtain the IRB/IEC's written approval/favorable opinion of the written informed consent form and any other information to be provided to the subjects, prior to the beginning of the study, and after any revisions are completed for new information.
- If informed consent is initially given by a subject's legally acceptable representative or legal guardian, and the subject subsequently becomes capable of making and communicating his or her informed consent during the study, consent must additionally be obtained from the subject.
- Revise the informed consent whenever important new information becomes available that is relevant to the subject's consent. The investigator, or a person designated by the investigator, should fully inform the subject or the subject's legally acceptable representative or legal guardian, of all pertinent aspects of the study and of any new information relevant to the subject's willingness to continue participation in the study. This communication should be documented.

The confidentiality of records that could identify subjects must be protected, respecting the privacy and confidentiality rules applicable to regulatory requirements, the subjects' signed ICF and, in the US, the subjects' signed HIPAA Authorization.

The consent form must also include a statement that BMS and regulatory authorities have direct access to subject records.

Subjects unable to give their written consent (eg, stroke or subjects with or severe dementia), may only be enrolled in the study with the consent of a legally-acceptable representative. The subject must also be informed about the nature of the study to the extent compatible with his or her understanding, and should this subject become capable, he or she should personally sign and date the consent form as soon as possible. The explicit wish of a subject who is unable to give his or her written consent, but is capable of forming an opinion and assessing information, to refuse participation in, or to be withdrawn from, the clinical study at any time should be considered by the investigator.

The rights, safety, and well-being of the study subjects are the most important considerations and should prevail over interests of science and society.

### **3 INVESTIGATIONAL PLAN**

#### **3.1 Study Design and Duration**

This study will enroll subjects with newly-diagnosed GBM, following surgical resection of the tumor. Tumor tissue will be evaluated for MGMT methylation by a central laboratory assay

through the CA209498 study. After enrolling in the CA209498 study, the subjects may enroll in the CA209548 study and begin the screening process while they wait for the MGMT results. The screening number assigned in the CA209498 IVRS will be the same subject number entered by the site to screen the subject into the CA209548 IVRS. Those with a MGMT status of methylated or indeterminate may be eligible to randomize in the CA209548 study. In order to randomize 693 eligible subjects, a total of approximately 780 subjects will be evaluated. For details, see [Section 3.1.1](#).

Subjects with a central laboratory result of MGMT-methylated or indeterminate may continue in the **screening phase**, in which eligibility for randomization will be documented and baseline demographic and disease information submitted; for details, see [Section 3.1.1](#).

When ready to begin study treatment, subjects will proceed to the **treatment phase** of the study; for details, see [Section 3.1.2](#). All subjects who enter the treatment phase, ie, all randomized subjects, will be followed for safety and tolerability, tumor progression, and survival. The first on-study contrast-enhanced MRI should be performed 4 weeks ( $\pm 7$  days) after completing radiation therapy, then subsequent scans should be every 8 weeks ( $\pm 7$  days) up to 24 months, then every 12 weeks until progression regardless of treatment schedule or dose delays. Tumor progression will be assessed using RANO described in [Section 5.4.2](#).

For the purposes of this protocol, each cycle duration is 2 weeks until 8 doses of 240 mg of nivolumab/placebo are complete. The remaining subsequent cycles (480 mg or placebo infusion, starting Week 17 in the absence of delays) are 4 weeks in duration. Cycle 9 should start 2 weeks after Cycle 8 begins.

[figure not shown]
After cessation of all study treatment for any reason, all randomized subjects will enter a **follow-up** phase. In the short-term, visits are defined for reporting of treatment-related adverse events. Following study unblinding, subjects who discontinue all treatment will not be followed for progression per RANO criteria, or for survival. For details on the follow-up phase, see [Section 3.1.3](#).

Baseline and all subsequent scans will be submitted to blinded independent central review (BICR) for review, once the subject is randomized and until study unblinding on 22-Dec-2020.

A Data Monitoring Committee (DMC) will meet regularly during the study until study unblinding to ensure that subject safety is carefully monitored, see [Section 7](#).

The study design schematic is presented in [Figure 3.1-1](#).

**Figure 3.1-1: Study Design Schematic**

[figure not shown]

Following unblinding, subjects may continue on nivolumab and/or temozolomide (if applicable) treatment, following all protocol procedures.

### 3.1.1 Screening Phase

Subjects will provide consent for enrollment and tumor submission in the peri-operative period in the CA209498 study so that MGMT status can be determined. Consent for enrollment in the CA209548 study will occur while waiting for the MGMT results to be obtained and randomization and study treatment will occur once MGMT status of methylated or indeterminate is known and eligibility is established (Figure 3.1.1-1).

**Figure 3.1.1-1: Screening and Randomization**

A centralized tumor tissue assay for MGMT is required as part of the CA209498 MGMT testing. Subjects will consent to the MGMT testing and the CA209548 study simultaneously. Following informed consent for both studies, subjects will be enrolled via a call to an IVRS system for the CA209498 MGMT testing, in order to obtain a subject number. Immediately after the subject number is obtained from the CA209498 IVRS, the site will then screen the subject into the CA209548 IVRS. The original subject identification number from CA209498 must be entered into the eCRF.

When possible, subjects should not be on corticosteroids at Screening. It is expected that corticosteroid therapy will be tapered to the maximum extent possible during this phase. Subjects who cannot tolerate tapering of steroids to < 20 mg prednisone or < 3 mg dexamethasone per day (or equivalent) are not eligible for randomization.

RT should begin within 42 days of surgical resection but may be delayed if clinically required. Typically, the time from screening procedure to treatment should not exceed 28 days, but may be longer if clinically indicated. If repeat resection to improve tumor control is performed for newly-diagnosed GBM prior to any other therapy (eg, upon referral to research site), the 42-day interval should restart at the time of this second surgery and a new post-operative MRI must be performed.

### 3.1.2 Treatment Phase

#### 3.1.2.1 Randomization and Initiation of Treatment

After eligibility has been confirmed, subjects who are clinically ready to begin study treatment (ie, recovered from surgery) will proceed to the treatment phase of the study via a second call into the IVRS system. At this call, subjects will be randomized 1:1 to receive radiotherapy, temozolomide plus nivolumab or radiotherapy, temozolomide plus placebo.

Randomization will be prospectively balanced (ie, stratified) according to post-operative MRI finding of “complete” versus “partial” resection. For the purposes of this study, a complete resection will be defined as ≤ 5 mm of contrast enhancement in any diameter on T1 images of the post tumor surgical region following surgical resection. A partial resection is defined as ≥ 10 mm

of residual contrast-enhancing tumor tissue on T1 images following surgical resection. Resections with a residual of > 5 and < 10 mm of enhancement will be defined as partial or complete by the investigator's best clinical judgment.

The total time elapsed from definitive surgery to initiation of RT should not exceed 42 days but may be delayed if clinically required. Typically, a delay from randomization to initiation of chemoradiation may be up to 7 days, or longer if clinically required. Subjects should begin nivolumab or placebo within 3 days after randomization and may be given at any time prior to chemoradiation start.

See [Sections 4.5.1](#) and [4.5.2](#) for details of dosing for nivolumab and temozolomide; for an overview of the treatment phase, see [Section 3.1.2](#).

### **3.1.2.2 Radiotherapy**

Radiation therapy should begin after substantial recovery from surgical resection, preferably not more than 42 days after surgery; however, treatment may be delayed if clinically required. External-beam RT to a total dose of 60 Gy will be administered in daily doses of 2 Gy, typically on a 5 days on / 2 days off schedule as appropriate for scheduling, over 6-7 weeks. Patients considered clinically inappropriate for full dose RT (60 Gy  $\pm$  5%) are not eligible, eg, due to older age, tumor location. RT is administered to the post-operative tumor volume plus a 2-3 cm margin, as directed by a radiation oncologist.

Radiation therapy planning and administration should follow currently-accepted guidelines. Additional details are provided in [Appendix 2](#). RT may be administered at a facility more convenient to the patient, but approval from Sponsor or designee must be obtained if not part of the same practice group as the investigative study site. For adverse events related to RT, see [Section 6](#).

Note: Suspected progression occurring during or within 12 weeks after RT may be "pseudoprogession"; in this setting, suspected progression should be confirmed prior to discontinuation of treatment. BMS Medical Monitor should be consulted.

### **3.1.3 Follow-up Phases**

The follow-up phase begins when the decision is made to discontinue a subject from study treatment, including for adverse events, for maximum clinical benefit (investigator decision), for subject request, disease progression, or another reason.

Following study unblinding, subjects who discontinue the experimental arm will be evaluated for adverse events with visits at 35 days ( $\pm$  7 days) and 115 days ( $\pm$  7 days) after last dose; for details, see [Table 5.1-3](#) and [Section 6](#). Subjects on placebo arm who discontinue study temozolomide treatment will be evaluated for adverse events with a visit at 35 days ( $\pm$  7 days) after last dose. All adverse events must be documented for a minimum of 100 days after discontinuation of nivolumab and for 30 days following discontinuation of temozolomide treatment, but drug-related toxicities should continue to be followed until they resolve, return to baseline, or are deemed irreversible. Subjects will not be followed for progression per RANO criteria, or for survival.

### **3.1.4 Overall Study Duration**

Enrollment and randomization of 693 subjects is expected to require approximately 25 months. One interim analysis and a final analysis on OS in the no baseline corticosteroid population were planned after approximately 236 and 337 deaths have been reported, respectively. Depending on assumptions, these analyses were anticipated to occur at approximately 45 and 69 months after first subject is randomized, respectively. Following study unblinding, the final analysis on OS will use the unblinding date for the data cut-off. One final analysis on PFS in the first 558 randomized subjects in all comers is planned after approximately 404 events have been reported. Depending on assumptions, this analysis is anticipated to occur at approximately 35 months after first subject is randomized. See Statistical Considerations, [Section 8](#) for details.

Data will be collected after the pivotal OS final analysis has occurred, for subjects remaining on treatment. The study will be closed when safety follow-up has completed for the last subjects to discontinue study treatment.

### **3.2 Post Study Access to Therapy**

At the conclusion of the study, subjects who continue to demonstrate clinical benefit will be eligible to receive BMS supplied study drug. Study drug will be supplied via an extension of the study, a rollover study requiring approval by responsible health authority and ethics committee or through another mechanism at the discretion of BMS. BMS reserves the right to terminate access to BMS supplied study drug if any of the following occur: a) the marketing application is rejected by responsible health authority; b) the study is terminated due to safety concerns; c) the subject can obtain medication from a government sponsored or private health program; or d) therapeutic alternatives become available in the local market.

### **3.3 Study Population**

For entry into the study, the following criteria **MUST** be met.

#### **3.3.1 Inclusion Criteria**

##### **1) Signed Written Informed Consent**

- a) Written informed consent and HIPAA authorization (applies to covered entities in the US only) obtained from the subject/legal representative prior to performing any protocol-related procedures
- b) Subjects must be willing and able to comply with scheduled visits, treatment schedule, laboratory testing, and other requirements of the study

##### **2) Target Population**

- a) Newly-diagnosed histologically-confirmed supratentorial glioblastoma (Grade IV malignant glioma by World Health Organization, including gliosarcoma) 
  - i) No treatment for GBM other than surgery
  - ii) Post-operative baseline MRI following consensus recommendations must be obtained prior to randomization. It is strongly recommended that this scan be obtained <72 hours or >14 days post-surgery in order to minimize artifact.

- b) Substantial recovery from surgical resection
  - i) No major ongoing safety issues (eg, infection requiring IV antibiotics) following surgery
  - ii) For subjects on corticosteroids at the time of Screening: able to taper steroids (preferably discontinued). Dose at randomization must be  $\leq 20$  mg prednisone or  $\leq 3$  mg dexamethasone daily (or equivalent). Subjects who do not need corticosteroids or able to taper down to  $\leq 20$  mg prednisone.
- c) As of Amendment 11, this criterion regarding screen fails from CA209498 is no longer applicable.
- d) Centrally confirmed (ie, third-party vendor) tumor MGMT-methylated or indeterminate from the CA209498 study
- e) Karnofsky Performance Status of  $\geq 70$  ([Appendix 3](#))
- f) Clinically appropriate for concomitant temozolomide plus RT, based on investigator judgment

### 3) Age and Reproductive Status

- a) Males and Females, age  $\geq 18$  years old
- b) Women of childbearing potential (WOCBP) must have a negative serum or urine pregnancy test (minimum sensitivity 25 IU/L or equivalent units of HCG) within 24 hours prior to the start of study drug
- c) Women must not be breastfeeding
- d) Women of childbearing potential (WOCBP) must agree to follow instructions for method(s) of contraception for the duration of the study treatment with nivolumab/placebo and 5 months after the last dose of study treatment (ie, 30 days [duration of ovulatory cycle] plus the time required for the investigational drug to undergo approximately five half-lives).
  - i) As of Amendment 11, this criterion has been merged into 3.d.
- e) As of Protocol Amendment 06, this criterion refers to TMZ treatment. Males who are sexually active with WOCBP must agree to follow instructions for method(s) of contraception for the duration of the study treatment with TMZ and for 6 months after the last dose of study treatment, or as noted in the locally applicable package insert, summary of product characteristics (SmPC), or similar document.
  - i) Males are encouraged to seek advice on cryoconservation of sperm prior to treatment, because of the possibility of irreversible infertility due to therapy with TMZ
- f) Azoospermic males and WOCBP who are continuously not heterosexually active are exempt from contraceptive requirements. However, WOCBP must still undergo pregnancy testing as described in this section.

Investigators shall counsel WOCBP, and male subjects who are sexually active with WOCBP on the importance of pregnancy prevention and the implications of an unexpected pregnancy.

Investigators shall advise on the use of highly effective methods of contraception ([Appendix 4](#)), which have a failure rate of < 1% when used consistently and correctly.

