## 4.1 Investigational Product

An investigational product, also known as investigational medicinal product in some regions, is defined a pharmaceutical form of an active substance or placebo being tested or used as a reference in a clinical study, including products already with a marketing authorization but used or assembled (formulated or packaged) differently than the authorized form, or used for an unauthorized indication, or when used to gain further information about the authorized form.

The investigational product should be stored in a secure area according to local regulations. It is the responsibility of the investigator to ensure that investigational product is only dispensed to study subjects. The investigational product must be dispensed only from official study sites by authorized personnel according to local regulations.

In this protocol, investigational products are nivolumab (BMS-936558), nivolumab placebo (0.9% sodium chloride for injection or 5% dextrose for injection), and temozolomide. Although not a medicinal product, Radiation Therapy is also considered part of study treatment.

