**Table 4.5-1: Selection and Timing of Dose**

Drug	Dose	Frequency of administration	Route of administration	Duration
Nivolumab/ Placebo (BMS-936558)	240 mg 480 mg, after 8 doses	Every 2 weeks, for 8 doses Every 4 weeks after 8 doses	30 minute intravenous (IV)	Until progression, unacceptable toxicity, or discontinuation from treatment
Temozolomide (TMZ)	75 mg/m  daily during RT then 150 mg/m  D1-5 for C1 and increased to 200 mg/m  D1-5 for C2-C6 as tolerated	Daily from first day of RT to last day of RT (not to exceed 49 days) then 4 week break followed by TMZ daily for 5 days every 28 days x 6 cycles a	Oral (PO)	Until completion of dosing, progression, unacceptable toxicity or discontinuation from treatment

a Additional cycles of temozolomide are permitted for subjects enrolled in Japan as well as others with written permission of Sponsor

Treatment modifications (eg, dose delay, reduction, or discontinuation) will be based on specific laboratory and adverse event criteria, as described in Sections 4.5.1 and 4.5.2. If the toxicity is considered related to either TMZ or nivolumab/placebo, both may be delayed, based on investigator judgment. However, if the toxicity is related to one or the other, then that one should be delayed or discontinued as appropriate. If the subject continues on either study drug, the visit schedule and assessments will continue as described in Table 5.1-2.

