Tumor Sample Submission at time of progression or suspected progression	At time of PD or suspected PD			If biopsy or surgical resection is performed at progression or suspected progression, a tumor sample (block or slides) should be submitted for central neuropathologic review

a If a subject discontinues nivolumab or placebo but continues TMZ, on-treatment assessments should continue. Chemistry panel will be collected every 4 weeks prior to TMZ dosing.

b Per RANO, assessment of disease progression during study requires that MRI scan be performed >12 weeks after RT; it is therefore recommended that second on-treatment scan be performed at least 84 days after completion of RT

Table 5.1-3: Treatment Follow-up and Survival Follow-up (CA209548)			
Procedure	Treatment Follow-upa	Survival Follow-upb	Notes
Targeted Physical Examination	X		Weight, BP, HR, RR, temperature and Karnofsky Performance Status
Adverse Events Assessment	X	X	Beyond 100 days from the last dose of study treatment subjects will be followed for ongoing nivolumab-related adverse events until resolved, return to baseline or deemed irreversible or until lost to follow-up, withdrawal of study consent, or discontinuation from the study.
Laboratory Tests	X		CBC w/differential, LFTs, BUN, creatinine and TSH at 35 days, repeat labs at 115 days visit if study drug-related toxicity persists
Pregnancy Test [WOCBP only]	X		Serum or urine pregnancy test (minimum sensitivity 25 IU/L or equivalent units of HCG)
Review of Concomitant Medications	X		
Tumor Assessment		X	Every 8 weeks ( $\pm$ 7 days) for 24 months and then every 12 weeks until progression, required only for subjects who did not progress on study treatment (eg, discontinued for AEs). Following study unblinding, tumor assessments will not continue for subjects who have discontinued study treatment. See Section 5.4 .
Tumor Sample Submission at time of progression or suspected progression	At time of PD or suspected PD		If biopsy or surgical resection is performed at the time of progression or suspected progression, a tumor biopsy sample (block or slides) should be submitted for central neuropathologic review; following study unblinding, this is optional.

Table 5.1-3: Treatment Follow-up and Survival Follow-up (CA209548)			
Procedure	Treatment Follow-upa	Survival Follow-upb	Notes

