On-treatment laboratory assessments include CBC w/differential to include ANC, done weekly during RT, then Day 1 and 22 during maintenance TMZ, then prior to each nivolumab/placebo cycle. Chemistry panel including AST, ALT, alkaline phosphatase, total bilirubin, albumin, BUN or serum urea, creatinine, Ca, Na, K, Cl, glucose will be performed every 4 weeks prior to nivolumab/placebo dosing or prior to TMZ dosing if the subject has been determined to be in the placebo arm. TSH, T3 and T4 (Free or Total, only if TSH abnormal) will be performed every 8 weeks for all subjects, or as clinically indicated. Pregnancy test will be performed every 4 weeks. Adverse events and laboratory values will be graded according to the NCI-CTCAE version 4.03.

On-study weight, Karnofsky performance status, and vital signs should be assessed every 2 weeks during RT followed by every 4 weeks in maintenance and at each on-study visit prior to dosing for nivolumab/placebo. Vital signs should also be taken as per institutional standard of care for subjects during and after dosing. The start and stop times of the infusions should be documented. Physical examinations are to be performed as clinically indicated. If there are any new or worsening clinically significant changes since the last exam, report changes on the appropriate non-serious or serious adverse events page.

Additional measures, including non-study required laboratory tests, should be performed as clinically indicated or to comply with local regulations. Laboratory toxicities (eg, suspected drug induced liver enzyme elevations) will be monitored during the follow-up phase via on site/local labs until all study drug related toxicities resolve, return to baseline or are deemed irreversible.

Evaluate participant immediately to rule out cardiac or pulmonary toxicity if participant shows cardiac or pulmonary-related signs (hypoxia, abnormal heart rate or changes from baseline) or symptoms (eg, dyspnea, cough, chest pain, fatigue, palpitations). Some of the previously referred to assessments may not be captured as data in the eCRF. They are intended to be used as safety monitoring by the treating physician. Additional testing or assessments may be performed as clinically necessary or where required by institutional or local regulations.

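### Criterion 3d names only nivolumab/placebo for women's contraception and leaves the start of the 5-month tail open; on one defensible reading it lapses before temozolomide ends

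*Protocol*

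**What the plan says.** Criterion 3d (Protocol Section 3.3.1, item 3) has women of childbearing potential follow contraception instructions "for the duration of the study treatment with nivolumab/placebo and 5 months after the last dose of study treatment". A parenthesis derives the five months from 30 days for an ovulatory cycle plus about five half-lives of an investigational drug, in the singular and unnamed. TMZ does not appear.

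Criterion 3e, for men, has the same sentence structure but names the other drug: "for the duration of the study treatment with TMZ and for 6 months after the last dose of study treatment, or as noted in" a local label or similar document.

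Section 4.1 defines the products more widely: "In this protocol, investigational products are nivolumab (BMS-936558), nivolumab placebo (0.9% sodium chloride for injection or 5% dextrose for injection), and temozolomide".

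TMZ without nivolumab/placebo is a planned state:

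- Section 4.5, on toxicity: "However, if the toxicity is related to one or the other, then that one should be delayed or discontinued as appropriate".
- Table 5.1-2, footnote a: "If a subject discontinues nivolumab or placebo but continues TMZ, on-treatment assessments should continue".
- Section 3.1.3, after unblinding: "Subjects on placebo arm who discontinue study temozolomide treatment will be evaluated for adverse events with a visit at 35 days".
- Section 5.3 schedules the chemistry panel "prior to TMZ dosing if the subject has been determined to be in the placebo arm".
- Table 4.5-1, footnote a, extends TMZ further: "Additional cycles of temozolomide are permitted for subjects enrolled in Japan as well as others with written permission of Sponsor".

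Appendix 4 expects women to use a highly effective method but gives a duration only under item 7 (abstinence): the whole of study treatment, plus five half-lives of a single unnamed drug, plus 30 days. The Amendment 07 rationale aligns contraception instructions with the TMZ label for male participants only. No visible text sets a TMZ-based period for women.

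**The concern.** The rule gives two different end dates for the same woman, depending on whether study treatment in the second half of the sentence means the drug just named or any study drug. In 3e the phrase evidently means the drug just named. Carried over to 3d, the women's requirement runs from nivolumab/placebo alone and can expire while TMZ is still being taken. The protocol treats TMZ as a reproductive risk for men, with a 6-month tail and a 6-month window for reporting partner pregnancies (Section 6.4). It would be odd to let the requirement lapse for women who take the drug themselves. At stake is the consistent application of a safety instruction across sites. No endpoint or estimate depends on it.

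**Working it through.** **The stated 5 months.** The visible text gives no half-life, so the figure cannot be reproduced. Solved backwards with 1 month = 30.4375 days (SAP Section 8), 5 months = 152.2 days and (152.2 − 30) / 5 = 24.4 days per half-life. One tail is thus built from one drug's half-life, and the drug is not named.

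**Inputs for the narrow reading.** Day 0 is the first nivolumab/placebo dose.

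- Nivolumab/placebo every 2 weeks for 8 doses (Table 4.5-1): dose n on day 14(n − 1), no delays.
- Radiotherapy (RT) with daily TMZ: starts up to 7 days after randomization (Section 3.1.2.1), taken here as day 7; 42 days typical, 49 maximum (Section 4.5.2.1).
- Then a 28-day break and six 28-day cycles with TMZ on days 1–5.

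**Formulas.** Requirement ends on day 14(n − 1) + 152. TMZ cycles start on day 7 + 42 + 28 + 28k for k = 0 to 5, that is, days 77, 105, 133, 161, 189 and 217. The last TMZ dose is on day 217 + 4 = 221.

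| Last nivolumab/placebo dose | Requirement ends (day) | Days before last TMZ dose (221) | Whole cycles uncovered | TMZ days uncovered |
|---|---|---|---|---|
| 1 | 152 | 69 | 3 | 15 |
| 2 | 166 | 55 | 2 | 10 |
| 3 | 180 | 41 | 2 | 10 |
| 4 | 194 | 27 | 1 | 5 |
| 5 | 208 | 13 | 1 | 5 |
| 6 | 222 | none (1 day after) | 0 | 0 |
| 7 | 236 | none (15 days after) | 0 | 0 |
| 8 | 250 | none (29 days after) | 0 | 0 |

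**Sensitivity to the schedule.**

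- Shortest (RT from day 0, 42 days): last TMZ dose on day 214. The gap after dose 1 is 214 − 152 = 62 days, and after dose 5 it is 214 − 208 = 6 days.
- Longest (RT from day 7, 49 days): last cycle starts on day 224 and the last TMZ dose is on day 228. The gap after dose 1 is 228 − 152 = 76 days. Dose 6 now also leaves one cycle uncovered, because day 222 precedes day 224.
- Delayed or additional TMZ cycles lengthen the gap.

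**Broad reading.** If the tail starts at the last dose of any study drug, it starts no earlier than the last TMZ dose, and the gap is zero.

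**Who could still be affected at Amendment 07 (02-Sep-2021).** Assume nobody was randomized after unblinding on 22-Dec-2020. In the extreme case, a woman first dosed that day on the longest schedule takes her last TMZ dose on 22-Dec-2020 + 228 days = 07-Aug-2021, 26 days before the amendment. Only women with delayed or extra cycles, or in a post-TMZ period, can remain. For placebo-arm women among them, assuming placebo had stopped by unblinding, the narrow requirement had ended by 22-Dec-2020 + 152 days = 23-May-2021, 102 days before the amendment.

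The extreme case is generous. By December 2020 over 80% of the required OS events had occurred: 0.80 × 337 ≈ 270, beyond the 236 that Section 8.1 placed about 20 months after the end of accrual. On planning assumptions, six on-schedule cycles were long finished.

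**The case against.** The strongest reply is that the broad reading is at least as well founded:

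- The tail clause in 3d drops the nivolumab/placebo qualifier.
- Section 4.1 counts TMZ as an investigational product and radiotherapy as part of study treatment.
- Section 3.1 and Table 5.1-2 speak of stopping all study treatment, so the term covers several components.
- Table 5.1-3, footnote a, counts safety follow-up from whichever drug was given last.
- Appendix 4 item 7 runs through the whole of study treatment.

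This stands. A reader might infer that a lapse during TMZ is the natural meaning of 3d, or that the protocol definitely stops requiring contraception while TMZ continues. The documents do not support either inference; they support two readings. The reply does not remove the ambiguity, though. The on-treatment clause still names nivolumab/placebo alone. The parallel sentence in 3e and the singular drug in the parenthesis favour the narrow reading, and the Protocol Summary, under study drug, sets study treatment apart from chemoradiation. Where the protocol wants a two-drug rule it writes one, as in the Protocol Summary on adverse event follow-up and in Table 5.1-3.

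A second reply is that other safeguards continue: pregnancy tests every 4 weeks, investigator counselling, reporting of any pregnancy and in most cases permanent discontinuation (Sections 3.5 and 6.4), and the TMZ label as a listed study material (Section 5.2). This also stands and limits the harm, but none of these sets a TMZ-based end date for women within the protocol.

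A third is reach. Nivolumab/placebo normally continues until progression or unacceptable toxicity, so a gap with on-schedule TMZ needs an early stop. That is correct.

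A reader might also infer that women are left short of a required period after TMZ. The documents give no such period for women, and the 6 months in 3e is for men, so no shortfall after TMZ can be measured from them.

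**Conclusion.** The point holds as a minor drafting ambiguity. On one defensible reading, women's required contraception ends 13 to 69 days before the last TMZ dose when nivolumab/placebo stops after doses 1 to 5 and six TMZ cycles are completed on schedule. On the other reading the gap is zero. The figures assume radiotherapy from day 7 for 42 days, no dose delays and 30.4375 days per month; the shortest and longest schedules move the dose-1 gap to 62 and 76 days.

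Confidence is moderate. The text merged into 3d at Amendment 11 and the consent pages cannot be seen and may name TMZ. The documents do not give the number of women concerned; at Amendment 07 it is probably small and may be zero. Sample size, alpha and all analyses are unaffected.

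**What to change.** Reword 3d so that women of childbearing potential use contraception during treatment with nivolumab/placebo and during treatment with TMZ, until the later of (i) 5 months after the last nivolumab/placebo dose and (ii) the period after the last TMZ dose given in the locally applicable package insert, SmPC or similar document. This follows the reference to local labelling in 3e and the later-of-two-drugs wording already used for safety follow-up. Bring Appendix 4 item 7 into line by naming both drugs.

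Because 3d is an entry criterion and enrolment is over, the rewording alone will not reach current subjects. Notify any site with women of childbearing potential still on TMZ or in the post-TMZ period.

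The cost is one sentence in 3d, one in Appendix 4, and a short letter to the few sites concerned, if there are any.
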